## 7.2.2 Efficacy

### 7.2.2.1 The ADHD-Rating Scale-5

The ADHD-RS-5 (DuPaul et al., 2016), the primary efficacy measure, is completed by the clinician and will be administered at baseline and each subsequent visit up to and including Visit 16/ET to capture the ADHD symptoms within each study period.

The ADHD-RS rating scale was developed to measure the behaviors of children with ADHD and is commonly used in clinical studies of ADHD (Buitelaar et al., 2007; Döpfner et al., 2006; Kratochvil et al., 2001; Michelson et al., 2001; Spencer et al., 2001). The ADHD-RS-5 consists of 18 items designed to reflect current symptomatology of ADHD based on DSM-5 criteria. Each item is scored on a 4-point scale ranging from 0 (reflecting no symptoms) to 3 (reflecting severe symptoms) with total scores ranging from 0-54. The 18 items may be grouped into 2 subscales: hyperactivity/impulsivity (9 items) and inattentiveness (9 items).

The ADHD-RS-5 should be completed by a clinician experienced in the evaluation of children with ADHD. Since the ADHD-RS-5 is an important measure for guidance in dosing decisions, the ADHD-RS-5 must be performed by an individual who is experienced with the scale. All individuals performing this assessment must be pre-approved by the sponsor or designee.

The title, version, and date of the ADHD-RS-5 used in this study are included in [Table 1](#).

### 7.2.2.2 Clinical Global Impression

The Clinical Global Impression Scale (Guy, 1976) permits a global evaluation of the subject's severity and improvement over time.

The Clinical Global Impression has been used extensively in clinical studies of ADHD (Michelson et al., 2001; Weiss et al., 2005; Wilens et al., 2001).

For Group B, the investigator will perform the CGI-S to rate the severity of a subject's condition on a 7-point scale ranging from 1 (normal, not at all ill) to 7 (among the most extremely ill subjects) at the baseline visit (Visit 2). Additionally at the baseline visit, the investigator should establish 3 target areas of improvement with the subject and the subject's parent/LAR. To generate the targets, an open-ended question such as "If this program of treatment works for your child, what things do you hope he/she will be doing better?" should be asked. Ratings will be completed with respect to ADHD symptoms.

For Group A and Group B, at each visit from Visit 3 up to and including Visit 16/ET, the investigator will assess the subject's improvement relative to the 3 target areas of improvement recorded at the baseline visit (Visit 2), on the CGI-I, a 7-point scale ranging from 1 (very much improved) to 7 (very much worse).

The CGI-S and CGI-I should be completed by a clinician experienced in the evaluation of children with ADHD. Since the CGI-I is an important measure for guidance in dosing decisions, the CGI-I must be performed by a principal investigator or subinvestigator who is

medically/clinically responsible for the subject and experienced with the scale. All individuals performing this assessment must be pre-approved by the sponsor or designee

The title, version, and date of the CGI-S and the CGI-I used in this study are included in [Appendix 3](#).

### **7.2.3 Safety**

The name and address of each third-party vendor (eg, clinical laboratory) used in this study will be maintained in the investigator's and sponsor's files.

#### **7.2.3.1 Medical and Medication History**

For subjects in Group A, any new medical history, ie, medical conditions that arose after the recording of the medical history in the antecedent study will be recorded at baseline (Visit 2).

For subjects in Group B, the investigator will take a complete medical history at the screening visit (Visit 1), including a medication history, and record all information gathered. The investigator must record all clinically or medically relevant information regardless of how much time has elapsed since the date of diagnosis.

With the consent of the subject and subject's parent/LAR, medical records from other treatment providers should be requested.

#### **7.2.3.2 Physical Examination (Including Height and Weight)**

For subjects in Group A, a full physical examination will be performed at the baseline visit (Visit 2) and at the end of treatment visit (Visit 16).

For subjects in Group B, a full physical examination will be performed at the screening visit (Visit 1) and at the end of treatment visit (Visit 16). Additionally, an abbreviated physical examination is required at the baseline visit (Visit 2) if >32 days have elapsed since the physical examination completed as part of the screening visit (Visit 1) was performed.

A physical examination will be performed by a qualified, licensed individual per local requirements (eg, physician, physician assistant, or nurse practitioner).

A full physical examination is composed of a review of the following body systems:

- General appearance
- Skin
- Head, eyes, ears, nose, and throat
- Spine/Neck/Thyroid
- Respiratory
- Cardiovascular
- Abdomen (including liver and kidneys)

- Musculoskeletal
- Neurological

If an abbreviated physical examination is required at the baseline visit (Visit 2), a review of the body systems will include the following:

- General appearance
- Respiratory
- Cardiovascular

For subjects in Group A, abnormalities identified at the baseline visit (Visit 2) will be documented in the subject's source documents. Changes after the baseline visit (Visit 2) will be captured as TEAEs, as determined by the investigator.

For subjects in Group B, abnormalities identified at the screening visit (Visit 1) will be documented in the subject's source documents. Changes after the screening visit (Visit 1) will be captured as TEAEs, as determined by the investigator.

#### **7.2.3.3 Adverse Event Collection**

At each study visit, parent/LAR and/or subject will be questioned in a general way to ascertain if AEs have occurred since the previous visit (eg, "Have you had any health problems since your last visit?"). Adverse events are collected from the time informed consent is signed. (Refer to Section 8.) This information should be collected prior to the completion of assessments at all study visits. In addition, any symptoms/conditions reported during assessments and deemed to be clinically significant by the investigator will be assessed as AEs.

#### **7.2.3.4 Vital Signs**

For subjects in Group A, measurements of oral or tympanic temperature, pulse, sitting blood pressure, and respiratory rate will be performed according to the schedule shown in Table 1. Measurement of temperature and respiratory rate will be performed as part of the last dose maintenance visit of the antecedent study.

For subjects in Group B, measurements of oral or tympanic temperature and sitting respiratory rate will be performed at the screening visit (Visit 1) only (Table 2). Measurements of sitting systolic and diastolic blood pressure and pulse will be performed at each visit to the site. Blood pressure, pulse, and respiratory rate will be determined after subjects have remained seated for a minimum of 3 minutes.

Blood pressure will be determined by age-appropriate cuff (the same equipment and the same arm should be used throughout the study). A blood pressure cuff appropriate for the subject's arm length and girth should be used for all blood pressure measurements. The age-appropriate cuff should be approximately two-thirds the length/width of the subject's arm (from elbow to shoulder). All blood pressure measurements should be performed throughout the study using the age-appropriate cuff and should be performed by the same study center personnel (if possible)

throughout the study. Three measurements should be obtained using the age-appropriate cuff with at least 2 minutes in between each collection for blood pressure and pulse and report the average of the 3 measurements for each parameter. The 3 individual measurements and the averaged reading should be recorded in the source documents.

Any clinically significant deviations from baseline (Visit 2) in vital signs that are deemed clinically significant in the opinion of the investigator are to be recorded as a TEAE.

#### **7.2.3.5 Height and Weight**

Height will be captured at baseline and each monthly treatment visit for all subjects. A calibrated stadiometer must be used for all height measurements. Height should be measured in inches or centimeters without shoes with the subject standing on a flat surface and with chin parallel to the floor. The body should be straight but not rigid. The subject's height should be recorded as accurately as possible and should be recorded to the nearest centimeter.

Weight will be captured at each visit to the site. The same calibrated scale must be used for all weight measurements. Weight should be measured in pounds or kilograms without shoes and with light clothing. Weight should be recorded as accurately as possible and should be recorded to the nearest 0.1 pound or 0.1 kilogram.

#### **7.2.3.6 Clinical Laboratory Evaluations**

All clinical laboratory assays will be performed according to the laboratory's normal procedures. Reference ranges are to be supplied by the laboratory and will be used to assess the clinical laboratory data for clinical significance and out-of-range pathological changes. The investigator should assess out-of-range clinical laboratory values for clinical significance, indicating if the value(s) is/are not clinically significant or clinically significant. Abnormal clinical laboratory values, which are unexpected or not explained by the subject's clinical condition, may, at the discretion of the investigator or sponsor, be repeated as soon as possible until confirmed, explained, or resolved.

Clinical laboratory evaluations will be performed as per schedule of assessments [Table 1](#) (Group A) and [Table 2](#) (Group B). Additionally, for subjects in Group B, clinical laboratory tests are required to be repeated before the baseline visit (Visit 2), and the results reviewed before enrolling the subject in the study, if >32 days have elapsed since the clinical laboratory evaluations completed as part of the screening visit (Visit 1) were performed.

\*Note: Blood and urine samples may be stored for up to but not longer than 25 years.

The following clinical laboratory evaluations will be performed:

### **Biochemistry and Endocrinology**

A blood sample (~3 mL) for biochemistry will be taken to assess the following parameters:

Total cholesterol	Calcium
Aspartate aminotransferase	Urate
Phosphorus	Blood urea nitrogen
Alanine aminotransferase	Total bilirubin
Sodium	Creatinine
Alkaline phosphatase	Glucose
Potassium	Albumin
Gamma-glutamyl transferase	Total protein
Thyroid-stimulating hormone	Lactate dehydrogenase
Thyroxine, Free	

### **Hematology**

A blood sample (~2 mL) for hematology will be taken to assess the following parameters:

Hemoglobin	Neutrophils
Hematocrit	Lymphocytes
Red blood cells	Monocytes
Platelet count	Eosinophils
White blood cell count – total and differential	Basophils
Mean corpuscular hemoglobin	Neutrophils Band Forms
Mean corpuscular hemoglobin concentration	Mean corpuscular volume

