11.2 Clinical Laboratory Variables

Descriptive statistics for clinical laboratory values (in SI units) and changes from Baseline to Visit 16/ET as well as shift tables from Baseline to Visit 16/ET for quantitative variables will be presented by treatment group of the antecedent studies, current treatment (SHP465) for each enrollment type, and overall for the following clinical laboratory variables:

Biochemistry and Endocrinology

Total cholesterol	Calcium
Aspartate aminotransferase	Urate
Phosphorus	Blood urea nitrogen
Alanine aminotransferase	Total bilirubin
Sodium	Creatinine
Alkaline phosphatase	Glucose
Potassium	Albumin
Gamma-glutamyl transferase	Total protein
Thyroid-stimulating hormone	Lactate dehydrogenase
Thyroxine, Free	

Hematology

Hemoglobin	Neutrophils
Hematocrit	Lymphocytes
Red blood cells	Monocytes
Platelet count	Eosinophils
White blood cell count – total and differential	Basophils
Mean corpuscular hemoglobin	Neutrophils Band Forms
Mean corpuscular hemoglobin concentration	Mean corpuscular volume

Urinalysis

Glucose	pH
Specific gravity	Urobilinogen
Blood	Color
Ketones	Leukocyte esterase
Protein	Nitrite
Bilirubin	

Microscopic examination will be conducted if protein and/or blood is/are detected during urinalysis. At a minimum the microscopic examination will consist of red blood cells, white blood cells, casts, and bacteria.

Clinical laboratory test values are potentially clinically important (PCI) if they meet either the low or high PCI criteria. The PCI criteria are listed in [Table 4](#) for subjects aged 4-5 years and [Table 5](#) for subjects aged 6-12 years. The number and percentage of subjects with post-baseline PCI values will be tabulated. The percentages will be calculated relative to the number of subjects with available baseline values and at least 1 post-baseline assessment. The numerator is the total number of subjects with at least 1 post-baseline PCI value. A supportive listing of subjects with post-baseline PCI values will be provided including the subject number, baseline, and post-baseline values.

Table 4 Criteria for Potentially Clinically Important Laboratory Tests for Subjects Aged 4-5 Years

Parameter	SI Unit	Lower Limit	Higher Limit
Biochemistry			
Albumin	g/L	< 30g/L	-
Aspartate transaminase (AST)	-	-	>3 x ULN
Alanine transaminase (ALT)	-	-	> 3 x ULN
Alkaline phosphatase			>2.5 x ULN
Blood urea nitrogen	mmol/L	-	> 10.7mmol/L or > 2.5 x ULN
Calcium	mmol/L	< 2	> 2.9
Total cholesterol	mmol/L	-	> 7.8

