Creatinine, serum	>1.5 x ULN (or alternatively >2mg/dl**, >176.8µmol/L)
Albumin	<3g/dl (<30g/L)
Total protein, plasma or serum	<5g/dl* or >9g/dl* (<50g/L or >90g/L)
Hematology	
Hemoglobin (He.)	<10g/dl (<100g/L)
Hematocrit	<32% or >45% (<0.32 or >0.45 Fraction of 1)
Blood Cells (RBC)	male: <2.5 x 10 ⁶ /µL; female: <2.0 x 10 ⁶ /µL (male: <2.5 x 10 ¹² /L; female: <2.0 x 10 ¹² /L)
Mean Corpuscular Hemoglobin (MCH)~	< 27pg or > 32pg
Mean Corpuscular Volume (MCV)~	< 70fL or > 110fL
Mean Corpuscular He. Concentration (MCHC)~	< 28g/dL or > 41g/dL (<280g/L or >410g/L)
Platelet count	<75 x 10 ⁹ /L or >500 x 10 ⁹ /L

Table 5 Criteria for Potentially Clinically Important Laboratory Tests for Subjects Aged 6-12 Years

Parameter	PCI Criteria
Biochemistry	
White Blood Cell Count (WBC)	<3 x 10 ⁹ /L or >16 x 10 ⁹ /L
Neutrophils Band Form	> 5%
Neutrophils	< 15%
Eosinophils	> 10%
Basophils	> 15%
Lymphocytes	> 80%
Monocytes	> 40%
ANC (%neutrophils x WBC count)	<1.3x10 ⁹ /L
Urinalysis	
Glucose	Positive Value (excluding trace)
Blood	Positive Value (excluding trace)
Ketones	Positive Value (excluding trace)
Protein	Positive Value (excluding trace)
Bilirubin	Positive Value (excluding trace)
Leukocyte Esterase	Positive Value (excluding trace)
Nitrite	Positive Value (excluding trace)

*The NCI has not specified a value, Shire physicians have agreed on lab values provided.

** Values taken from the Reviewer Guidance, Conducting a Clinical Safety Review of a New Product Application and Preparing a Report on the Review, Table 7.1.7.3.2.1 pp 70-72. US DHHS FDA CDER, February 2005.

-These values were taken from Clinical Laboratory Diagnostics, ed. L. Thomas, MD, Frankfurt, Germany, 1998.

ULN: Upper limit of normal value provided by the laboratory

Age is calculated from the informed consent date from antecedent studies for Group A and from the informed consent date from SHP465-308 for Group B.

All laboratory data will be listed for the Safety Set.

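### SAP Table 5 (ages 6 to 12): the MCH limit is inconsistent with the MCV and MCHC limits beside it, so a child well inside both can still be counted as potentially clinically important

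*Protocol*

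**What the plan says.** Protocol section 7.2.3.6 lists MCH, MCV and "Mean corpuscular hemoglobin concentration" among the hematology parameters, and SAP section 11.2 repeats the list. The protocol sets no limits. They are in SAP Table 5, for ages 6 to 12: MCH ("< 27pg or > 32pg"), MCV ("< 70fL or > 110fL") and MCHC ("< 28g/dL or > 41g/dL (<280g/L or >410g/L").

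The three rows carry the same mark. The footnote that appears to belong to it gives one laboratory textbook as the source ("These values were taken from Clinical Laboratory Diagnostics"). The SAP does not say what share of healthy children each range is meant to cover, or why one range is so much tighter than the others.

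Under section 11.2 a laboratory value is PCI "if they meet either the low or high PCI criteria", so each parameter is judged alone. On reporting: "The number and percentage of subjects with post-baseline PCI values will be tabulated". The denominator is the "number of subjects with available baseline values and at least 1 post-baseline assessment", so a baseline value must exist but need not be normal. SAP section 18.4 adds that every post-baseline assessment, repeats included, feeds the PCI determination.

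**The concern.** MCH is hemoglobin per red cell, MCV is hematocrit per red cell, and MCHC is hemoglobin per unit of hematocrit. MCH is therefore the product of the other two, apart from units. If a table accepts any MCV in one range together with any MCHC in another, it has in effect accepted the products. Table 5 then rejects many of those products through a separate MCH row.

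Laboratory results are part of the primary safety objective. All subjects receive open-label SHP465 and the study has no concurrent control, so a background rate of MCH flags cannot be set against a comparator. A count that includes children whose MCH sat at the same value before and during treatment is harder to read as a drug effect.

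**Working it through.** **Inputs from SAP Table 5.** Not flagged: MCH 27 to 32 pg, MCV 70 to 110 fL, MCHC 28 to 41 g/dL. Unit check: 28 and 41 g/dL equal 280 and 410 g/L, as printed. The limits are set values, so there is no calculated figure in the plan to reproduce.

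**Identity.** MCH (pg) = MCV (fL) × MCHC (g/dL) / 100.

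**1. Outer bound over both component ranges.** 70 × 28 / 100 = 19.6 pg and 110 × 41 / 100 = 45.1 pg. Each bound needs both indices at their limit at once.

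**2. At a fixed MCHC (assumed; the documents give no typical value).**

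| MCHC (g/dL) | MCH over MCV 70 to 110 fL (pg) | MCV at MCH 27 and 32 pg (fL) |
|---|---|---|
| 31 | 21.7 to 34.1 | 87.1 and 103.2 |
| 33 | 23.1 to 36.3 | 81.8 and 97.0 |
| 36 | 25.2 to 39.6 | 75.0 and 88.9 |

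At MCHC 33, MCV values of 70 to 81.8 fL and 97.0 to 110 fL pass the MCV row but are flagged on MCH.

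**3. Relative width around the midpoint.** MCV 90 ± 20 is ± 22%; MCHC 34.5 ± 6.5 is ± 19%; MCH 29.5 ± 2.5 is ± 8.5%. The product is held to a tighter band than either factor.

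**4. One example.** MCV 80 and MCHC 33 give MCH = 80 × 33 / 100 = 26.4 pg, which is flagged. For any hematocrit that Table 5 accepts (32% to 45%), this child has hemoglobin of 0.32 × 33 = 10.56 to 0.45 × 33 = 14.85 g/dL (105.6 to 148.5 g/L; the limit is <100 g/L). The red cell count is 0.32 / 80 fL = 4.0 to 0.45 / 80 fL = 5.6 × 10¹²/L (limits <2.5 for males, <2.0 for females). Every other red-cell row is passed.

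**5. How often it might happen (assumption only).** The documents give no MCH distribution, no laboratory reference range and no expected PCI rate. The share outside 27 to 32 pg for a normal distribution, per draw, is:

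| Mean (pg) | SD 1.0 | SD 1.5 | SD 2.0 |
|---|---|---|---|
| 28 | 15.9% | 25.6% | 33.1% |
| 29 | 2.4% | 11.4% | 22.5% |
| 29.5 | 1.2% | 9.6% | 21.1% |
| 30 | 2.4% | 11.4% | 22.5% |

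If 27 to 32 pg were a central 95% range, the share would be 5% per draw. Protocol Table 4 (blood volume) plans three hematology samples. Read as one baseline and two post-baseline draws, the share with at least one flag would be at most 1 − 0.95² = 9.75%, since repeat values in one child are correlated. At planned enrollment, ages 6 to 12 number at most about 145 − 40 = 105 (protocol) or 80 − 40 = 40 (SAP), so 5% is about 5 or 2 children per draw. Early termination of the study would reduce the number of draws.

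**The case against.** The strongest reply is that little depends on this row. PCI is a descriptive screen, no formal tests are planned, and investigators judge clinical significance against the laboratory's own ranges. The supporting listing shows each subject's baseline beside the post-baseline value, so a trivial drift can be recognized. Any fixed cut-off also turns some small drifts into flags. All of this stands, and it keeps the point minor. It does not remove the inconsistency, because the tabulated percentage is what a reader sees first and it does not separate stable values from changed ones.

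The limits also have a cited source that cannot be inspected here, so none of the three can be called wrong on its own terms. That too stands: the finding is that they do not fit together, not that 27 to 32 pg is a mistaken range.

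Finally, 19.6 to 45.1 pg exaggerates the gap, since it multiplies two extremes. That is correct, and the fairer comparison is at a fixed MCHC. The mismatch remains there: 23.1 to 36.3 pg against 27 to 32 pg at MCHC 33.

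**Conclusion.** The MCH limit in Table 5 is inconsistent with the MCV and MCHC limits in the same table. A child well inside both component limits, and inside every other red-cell limit, can be tabulated and listed as PCI on MCH, whether or not the value has changed from baseline. This rests on the SAP's limits and the definitions of the indices.

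The number of children affected is not known. Under assumed means of 28 to 30 pg and SDs of 1 to 2 pg, it is about 1% to 33% per draw; a mean of 27 pg would give about 50%.

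Several stronger readings are tempting but unsupported:
- **Many healthy children will be flagged, or MCH flags will dominate the hematology PCI table.** Both need an MCH distribution that the documents do not give, and the second also needs rates for the other rows.
- **Most accepted MCV values are flagged.** At MCHC 33 the flagged part is (11.8 + 13.0) / 40 = 62% of the 70 to 110 fL interval, but that is a share of an interval and not of children.
- **The MCV row would flag almost nobody by comparison.** At MCHC 34.5, MCV 70 fL equals MCH 24.15 pg. With a mean of 28 and SD of 2.0 that is z = −1.93, or about 2.7% below the limit.
- **The MCH row makes the two age groups non-comparable.** SAP Table 4 (ages 4 to 5) has no row for any of the three indices and differs from Table 5 on other parameters too, so removing the MCH row would not make the tables comparable.

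**What to change.** Remove the MCH row from the Table 5 PCI criteria and keep MCH in the descriptive and shift tables. Alternatively, the sponsor should reconcile the MCH, MCV and MCHC limits so that all three are on the same basis, and state that basis in the footnote. Simply widening MCH to the outer bound of 19.6 to 45.1 pg would add nothing, because any MCH outside it must already breach the MCV or MCHC limit.

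Removal changes one row of a SAP table and no data collection. The hemoglobin, hematocrit, red cell count, MCV and MCHC flags remain. The cost is that an isolated MCH shift with normal hemoglobin, MCV and MCHC would no longer be flagged as PCI. It would stay visible in the descriptive and shift tables and in the laboratory listing.

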## Urinalysis

A urine sample (~10 mL) for urinalysis will be collected to assess the following parameters:

Glucose	pH
Specific gravity	Urobilinogen
Blood	Color
Ketones	Leukocyte esterase
Protein	Nitrite
Bilirubin	

If urinalysis detects protein and/or blood, a microscopic examination will be conducted. The microscopic examination will consist of red blood cell, white blood cell, casts, and bacteria.

For Group B subjects, a urine drug and alcohol screen will be conducted at the screening visit (Visit 1). As a reminder, a urine drug screen should be repeated at the baseline visit (Visit 2) if more than 32 days have elapsed since the screening visit (Visit 1). The following drugs/drug classes will be tested:

